4.4 Analysis populations

4.4.1 Full analysis set (FAS)

The full analysis set (FAS) will include all randomized subjects. Following the intent-to-treat (ITT) principle, subjects will be analyzed according to the treatment they are assigned to at randomization regardless of the treatment actually received.

4.4.2 Per-protocol set (PPS)

The PPS consists of all subjects in the FAS who received the allocated treatment and did not have any major protocol deviations (section 4.3).

5 Trial Population

5.1 Screening data

The number of screened, eligible, consenting and randomized patients will be presented.

5.2 Eligibility

Inclusion and exclusion criteria are defined in the study protocol¹. The number and proportion of patients not fulfilling each criteria will be presented. The reasons for not obtaining an informed consent will be shown.

5.3 Recruitment

A CONSORT patient flow diagram will be drawn following the CONSORT 2010 standards (<http://www.consort-statement.org/consort-2010>).

5.4 Withdrawal/follow-up

All withdrawals and losses to follow-up will be listed with the time points and reasons (if available).

5.5 Baseline patient characteristics

Evaluations of the baseline characteristics will be based on the FAS. They will be presented in a descriptive summary table by treatment group—continuous variables as mean and standard deviation or median and quartiles, and categorical variables as absolute and relative frequencies. No statistical comparisons of patient characteristics at baseline will be performed.

5.5.1 Sociodemographics

Sociodemographics are collected on eCRFs “Baseline Characteristics”.

Table 3: Sociodemographics.

Description	Variable	Type
Age	patient_age	Continuous: years
Gender	gender	Binary: Male, Female
Nationality*	nationality	Categorical: Switzerland, Germany, France, Italy, Spain/Portugal, East Europe, Africa, Other, Unknown
Living status	living_st	Categorical: With spouse/partner, With another person, Alone, Unknown
Living place type*	living_type	Categorical: Home, Protected apartment, Nursing home, Other, Unknown
Nurse visits at home†	nurse_home	Categorical: No, Yes, Unknown
Support at home for cleaning†	support_home_cleaning	Binary: No, Yes
Support at home to buy grocery†	support_home_housing	Binary: No, Yes
Support at home for eating†	support_home_eating	Binary: No, Yes

Description	Variable	Type
Source of revenue	work	Categorical: Employed, Self-employed, Unemployed, Retired, Invalidity insurance, Social, Other, Unknown
Health insurance*	insur	Categorical: Base, Base+compl, Semi-private, Private, Other, No insurance
Patient left against medical advice	patient_left	Binary: No, Yes

*Further specifications are given as free text and will be listed only

†Not applicable if living type is nursing home

5.5.2 Index admission and HOSPITAL score

Characteristics of index admission are collected on eCRFs “Baseline Characteristics” and “Costs at Index Diagnoses”. Components of the HOSPITAL score are collected on eCRF “Eligibility” and—in case of changes from screening to baseline—on eCRF “Baseline Characteristics”.

Table 4: Index admission and HOSPITAL score

Description	Variable	Type
Patient discharged alive	discharged_alive	Binary: No, Yes
Destination after discharge*	discharged_destination	Categorical: Home, Nursing home, Other acute care Hospital, Acute geriatric, Rehab, Palliative care, Other, Unknown
Length of stay	computed_nbdays	Continuous: days
Costs (in CHF) of the index hospitalisation	costs_indexhosp	Continuous: CHF
HOSPITAL score		
Last hemoglobin level available before discharge	hb_last or hb_last_2†	Continuous: g/l
Last sodium level available before discharge	na_last or na_last_2†	Continuous: mmol/l
Type of admission	adm_elect or adm_elect_2†	Binary: Elective, Non elective
Number of hospitalization at the same hospital in the last 12 months	prevhosp or prevhosp_2†	Integer
Length of stay of current hospitalization (in days).	los_index or los_index_2†	Continuous: days
Active cancer defined as under treatment, or if remission < 5 years	cancer or cancer_2†	Binary: No, Yes
Hospital score (simplified)	hosp_score_simple or hosp_score_simple_2†	Integer 0-12

*Further specifications are given as free text and will be listed only

†The former is used if the HOSPITAL score did not change from screening to baseline, the latter if it did change. A change is documented by variable hospital_change on eCRF “Baseline Characteristics”

5.5.3 Index diagnosis

Information about the index diagnosis is collected on eCRF “Index Diagnosis”.

Table 5: Index diagnosis and comorbidities.

Description	Variable	Type
Main diagnosis category*	main_dx_at	Categorical: Heart failure, Acute ischemic heart disease, Arrhythmia, Venous thromboembolism, Stroke/TIA, COPD exacerbation, Pneumonia, Other infection, sepsis, Gastro-intestinal disorder, Liver disorder, Renal disorder, Nutritional or metabolic disorder, Adverse drug event, Neoplasm, Epilepsy, Other
Secondary diagnoses and comorbidities*		
Chronic heart failure	comorbidities__1	Binary: Unchecked, Checked
Coronary disease	comorbidities__2	Binary: Unchecked, Checked
Atrial fibrillation	comorbidities__3	Binary: Unchecked, Checked
Peripheral artery disease	comorbidities__4	Binary: Unchecked, Checked
Diabetes	comorbidities__5	Binary: Unchecked, Checked
Dementia	comorbidities__6	Binary: Unchecked, Checked
COPD	comorbidities__7	Binary: Unchecked, Checked
Active cancer	comorbidities__8	Binary: Unchecked, Checked
Chronic renal failure	comorbidities__9	Binary: Unchecked, Checked
Liver cirrhosis	comorbidities__10	Binary: Unchecked, Checked
Drug or Alcohol Abuse	comorbidities__11	Binary: Unchecked, Checked
Epilepsy	comorbidities__12	Binary: Unchecked, Checked
Any treated psychiatric disease	comorbidities__13	Binary: Unchecked, Checked
Letter of discharge has been collected	letter_disch_late	Binary: No, Yes

*Main and secondary diagnoses are also documented as free text (variables main_dx and dx_1_dx20), which will be listed only.

5.6 Procedural characteristics

Procedural characteristic include the components of the transitional care intervention and are collected for the transition care group only. The pre-discharge component of the intervention is documented at baseline (visit 1) on eCRF “Pre-discharge component”, the follow-up phone calls (visit 2 and visit 3) on eCRFs “Follow-up call 1 (Day 3)” and “Follow-up call 2 (Day 14)”. Evaluations of the procedural characteristics will be based on the FAS. They will be presented in a descriptive summary table—continuous variables as mean and standard deviation or median and quartiles and categorical variables as absolute and relative frequencies.

Table 6: Procedural characteristics: pre-discharge components.

Description	Variable	Type
Basic information about her/his main diseases has been performed?	pat_info	Binary: No, Yes
Which information about those comorbidities have been given to the patient?		
Heart failure	inf_shee_giv_1	Binary: Unchecked, Checked
Coronary disease	inf_shee_giv_2	Binary: Unchecked, Checked
Peripheral artery disease	inf_shee_giv_3	Binary: Unchecked, Checked
Atrial fibrillation	inf_shee_giv_4	Binary: Unchecked, Checked
Chronic obstructive lung disease	inf_shee_giv_5	Binary: Unchecked, Checked
Stroke	inf_shee_giv_6	Binary: Unchecked, Checked
Gastrointestinal bleeding	inf_shee_giv_7	Binary: Unchecked, Checked
Chronic renal failure	inf_shee_giv_8	Binary: Unchecked, Checked
Liver cirrhosis	inf_shee_giv_9	Binary: Unchecked, Checked
Thromboembolism	inf_shee_giv_12	Binary: Unchecked, Checked
Diabetes	inf_shee_giv_13	Binary: Unchecked, Checked
Other*	inf_shee_giv_88	Binary: Unchecked, Checked
No listed comorbidity	inf_shee_giv_0	Binary: Unchecked, Checked
Medication reconciliation has been performed and explanation about medication list?	med_reco	Binary: No, Yes
Have you noticed any medication discrepancy that needed to be transmitted to the medical team?	med_reco_disc	Binary: No, Yes
Patient education about general health recommendation has been performed?	pat_educ	Binary: No, Yes
Dependence Level: score of the Katz Index	katz_ind	Integer: 0-6
Post discharge follow-up visit to the treating physician has been planned?*	folup_plan	Binary: No, Yes
Discharge summary sent to the treating physician	dis_sumpcp	Binary: No, Yes
Barriers to a safe discharge, including patient's ability to carry out the discharge plan has been assessed	finalcheck	Binary: No, Yes

*Further specifications are given as free text and will be listed only.

Table 7: Procedural characteristics: follow-up call 1 (Day 3) and follow-up call 2 (Day 14).

Description	Variable	Type
Patient reached by phone	reach_phone_d3 or reach_phone_d14†	Binary: No, Yes
Reason why the patient wasn't reached*	reas_pat_notre_d3 or reas_pat_notre_d14†	Categorical: Death, No answer, Other
Death source of information*	death_sourceinfo_d3 or death_sourceinfo_d14†	Categorical: Next of kin, Treating physician, Hospital, Death certificate, Other
Death was due to an accident/trauma?	trauma_death_d3 or trauma_death_d14†	Categorical: No, Yes, Unknown
Cause of death (according to certificate of death if possible)	cause_death_d3 or cause_death_d14†	Free text
Condition improved since discharge	cond_impr_d3 or cond_impr_d14†	Categorical: No, or rather no, Yes or rather yes, Stable, New symptom
Since your discharge of the hospital, do you have more pain?	morepain_d3 or morepain_d14†	Binary: No, Yes
How does the mobility/walking distance change since discharge?	red_wal_dis_d3 or red_wal_dis_d14†	Categorical: Mobility/walking distance improved, Mobility/walking remained about the same, Mobility/walking decreased, Not able to evaluate
Capacity to prepare meals alone?	cap_meal_d3 or cap_meal_d14†	Binary: No, Yes
Weight trend over the last days/weeks	wei_tren_d3 or wei_tren_d14†	Categorical: Increased, Reduced, Stable, Unknown
Glucose values most often†	glu_val_tre_d3 or glu_val_tre_d14†	Categorical: Between 4-10, >10, Between 10-15, >15, Unknown
Do you take your medication as prescribed?	medicasprescribed_d3 or medicasprescribed_d14†	Binary: No, Yes
Is there any medication discrepancy between current list and list of discharge?	med_discr_d3 or med_discr_d14†	Binary: No, Yes
Presence of any of those medications?	pre_med_d3 or pre_med_d14†	Categorical: Anticoagulants, Narcotics and opiates, Sedatives, Insulin
Did any of these Adverse Event occur since discharge?		
Dizziness	adv_dru_ev_d3_1 or adv_dru_ev_d14_1†	Binary: Unchecked, Checked
Bleeding	adv_dru_ev_d3_2 or adv_dru_ev_d14_2†	Binary: Unchecked, Checked
Hypoglycemia	adv_dru_ev_d3_3 or adv_dru_ev_d14_3†	Binary: Unchecked, Checked
Delirium	adv_dru_ev_d3_4 or adv_dru_ev_d14_4†	Binary: Unchecked, Checked
Lethargy / Oversedation	adv_dru_ev_d3_5 or adv_dru_ev_d14_5†	Binary: Unchecked, Checked
Nausea / vomiting	adv_dru_ev_d3_6 or adv_dru_ev_d14_6†	Binary: Unchecked, Checked
Fall	adv_dru_ev_d3_7 or adv_dru_ev_d14_7†	Binary: Unchecked, Checked

Description	Variable	Type
None	adv_dru_ev_d3_0 or adv_dru_ev_d14_0†	Binary: Unchecked, Checked
Patient had doctor's office visit since discharge	pcp_visit_d3 or pcp_visit_d14†	Categorical: No, Yes as planned, Yes as new appointment
Reason why the patient didn't have any treating physician visit since discharge*	reas_no_pcp_d3 or reas_no_pcp_d14†	Categorical: Visit is planned, Patient didn't want/ couldn't, Treating physician couldn't/not available, Other, Unknown
Suggestion to see the treating physician was necessary during this follow-up call	sug_see_pcp_d3 or sug_see_pcp_d14†	Binary: No, Yes
Patient education about her/his diseases has been refreshed	patient_education_d3 or patient_education_d14†	Binary: No, Yes

*Further specifications are given as free text and will be listed only

†For follow up call 1 and 2, respectively.

‡Only for patients with diabetes

6 Analysis

6.1 Outcome definition

6.1.1 Primary outcome

The primary outcome is the number of patients who have an unplanned readmission or die within 30 days after discharge.

6.1.2 Secondary outcomes

- Number of deaths within 30 days after discharge
- Number of patients with unplanned readmission within 30 days after discharge
- Time to first unplanned readmission or death within 30 days
- Main cause of readmission or death
- Post-discharge health care utilization within 30 days after discharge from index hospitalization:
 - number of unplanned hospital readmissions
 - number of planned hospital readmissions
 - total number of unplanned days of hospitalizations
 - total number of planned days of hospitalizations
 - number of emergency room visits
 - number primary care provider visits
- Patient's perspective (satisfaction) on quality of transition of care between hospital and home assessed by the three-item care transition measure (CTM-3) at 30 days
- Costs of readmission at 30 days

6.2 Outcome derivation

Table 8: Derivation of primary and secondary outcomes.

Outcome	eCRF sheet	Variable	Variable type	Derivation	Outcome type
Primary: Unplanned readmission or death within 30 days after discharge	Baseline Characteristics	discharged_alive	Binary: No, Yes	discharged_alive==No or	Binary
	Follow-up calls	reas_pat_notre_d3, reas_pat_notre_d14	Categorical: Death, No answer, Other	reas_pat_notre_d3==Death or	
	Outcomes 30 days	death_d30	Binary: No, Yes	reas_pat_notre_d14==Death or	
Deaths within 30 days after discharge	Baseline Characteristics	unplanned	Integer: 0-6	death_d30==Yes or	Binary
		discharged_alive	Binary: No, Yes	unplanned>=1	
		reas_pat_notre_d3, reas_pat_notre_d14	Categorical: Death, No answer, Other	discharged_alive==No or	
Outcomes 30 days	Follow-up calls	death_d30	Binary: No, Yes	reas_pat_notre_d3==Death or	Binary
		reas_pat_notre_d14	Categorical: Death, No answer, Other	reas_pat_notre_d14==Death or	

Outcome	eCRF sheet	Variable	Variable type	Derivation	Outcome type
Unplanned readmission within 30 days after discharge	Outcomes 30 days	unplanned	Integer: 0-6	unplanned>=1	Binary
Time to first unplanned readmission or death	Baseline Characteristics	disch_date_index, baseline_death	Date: dmy	Time: min(30, min[baseline_death, date_death_d3, date_death_d14, date_death_d30 unplanned_in_1, lcontact_date] – disch_date_index)	Time-to-event
	Follow-up calls	date_death_d3, date_death_d14	Date: dmy		
	Outcomes 30 days	date_death_d30, unplanned_in_1	Date: dmy		
	End of Study	lcontact_date	Date: dmy	Failure: Primary==Yes	
Main cause of readmission or death	Follow-up calls	cause_death_d3, cause_death_d14	Free text	Tabulated free text fields will be manually categorized	Categorical
	Outcomes 30 days	dx_read30, cause_death_d30	Free text		
Number of unplanned hospital readmissions	Outcomes 30 days	unplanned	Integer: 0-6	-	Count
Number of planned hospital readmissions	Outcomes 30 days	planned_readmission	Integer: 0-8	-	Count
Total number of unplanned days of hospitalizations	Outcomes 30 days	unplanned_x_in, unplanned_x_out	Date: dmy	unplanned_x_out – unplanned_x_in	Count
Total number of planned days of hospitalizations	Outcomes 30 days	tot_rehosp_days_planned	Continuous: days	-	Count
Number of emergency room visits	Outcomes 30 days	nb_edvisits	Integer	-	Count
Number primary care provider visits	Outcomes 30 days	nb_pcpvisits	Integer	-	Count
Offset for count variables	Baseline Characteristics	disch_date_index, baseline_death	Date: dmy	min(30, min[baseline_death, date_death_d3, date_death_d14, date_death_d30 lcontact_date] – disch_date_index)	Continuous
	Follow-up calls	date_death_d3, date_death_d14	Date: dmy		
	Outcomes 30 days	date_death_d30	Date: dmy		
	End of Study	lcontact_date	Date: dmy		
Patient's perspective (satisfaction) on quality of transition of care between hospital and home (CTM-3)	Outcomes 30 days	ctm1, ctm2, ctm3	Binary: No, Yes	ctm1==Yes & ctm2==Yes & ctm3==Yes	Binary
Costs of readmission	Costs at Outcomes 30 days	costs_30d	Continuous: CHF	-	Continuous

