2.8 Blinding

Most of the study personal including PI, study nurses, statistician and data manager will not be blinded. However, the study nurses collecting the outcomes or working on data cleaning will be blinded to the group allocation.

3 Data management

The CRFs in this trial are implemented electronically using a dedicated electronic data capturing (EDC) system (REDCap, <https://www.project-redcap.org/>). The EDC system is activated for the trial only after successfully passing a formal test procedure. All data entered in the CRFs are stored on a Linux server in a dedicated mySQL database. Responsibility for hosting the EDC system and the database lies with CTU Bern.

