4.2 Confidence intervals and p-values

A level of statistical significance of 5% will be used. All statistical testing will be two-sided. All tests will be accompanied by an effect measure (transitional care vs usual care) with a 95% confidence interval (95% CI).

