6.4 Missing data

The number of patients with non-missing observations will be reported for each outcome.

Missing data may occur due to drop-outs or deaths. The former will lead the absence of all outcome information as outcomes are only assessed once. Since the follow-up is very short we do not expect a lot of drop-outs and it is unlikely that these patients did have a readmission or died. Therefore, we will assume that drop-outs did not have a readmission and did not die. For survival analyses they will be censored at one day. For count outcomes they will be assumed to have no observed event and an offset of one day. For patient satisfaction multiple imputations will be used (section 6.4.1). If the amount of drop-outs is larger than 5%, we will do a sensitivity analysis in which the primary outcome (unplanned readmission or death) will be multiply imputed as a binary variable (section 6.4.1).

Death will not lead to missing data for the primary outcome, 30-day deaths and time to primary outcome. For 30-day unplanned readmission, death is a competing event and the cumulative incidence at 30 days will be used (section 6.3.1.2). Count outcomes will be handled by including the observation time as offset in the Poisson regression. For patient satisfaction multiple imputations will be used (section 6.4.1). In a sensitivity analysis, the worst possible outcome will be assigned to deaths (i.e. a negative respond to all question of the CTM-3).

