6.7 Quality control

A second statistician will reproduce the analysis of the primary outcome (for both the FAS and the PPS) based on the exported data. The risk difference and the 95% confidence interval should not differ by more than 0.01, the p-value by 0.001. Otherwise, the reason for the difference will be determined and a consensus must be reached.

7 Changes from the protocol

The SAP is consistent with principle features of the statistical methods described in the protocol. The following deviations were made:

Table 10: Changes from protocol

Header	Change	Reason
Blinded analysis	Blinded analysis not implemented	The allocation can immediately be seen from the eCRFs because only patients in the intervention group have follow up phone calls. It would therefore need an extra statistician that carefully prepares the data so that it is not possible to see the allocation. Given the open-label nature of the study and the straightforward analysis this additional effort seems not to be justified.
Secondary outcome "Medication adherence: 4-item Morisky Medication Adherence Scale (MMAS-4)".	Removed	High license fees would incur
Secondary endpoint "Number of planned hospital readmissions" and "Total number of planned days of hospitalizations"	Added	Information about the planned readmissions is of interest but was not considered in the protocol.
Test for the analysis of primary and binary secondary outcome	Stratified Cochran-Mantel-Haenszel test instead of simple chi-squared test	Stratification factor should be considered in the analysis
Subgroup HOSPITAL score	Categories 4 or 5 vs ≥ 6 instead of 5 or 6 vs ≥ 7	Categories correspond to stratification of the randomization
Subgroup clinical site	Added	Used as stratification factor in randomization
Subgroups cancer, living place, living status and health insurance	Added	Of interest, not mentioned in protocol

References

¹ Clinical trial protocol: Transition care intervention targeted to high-risk patients to reduce readmission (TARGET-READ): A randomized controlled trial, Version 1.1, 13.02.2018

² SOP Data preparation and programming, CS_STA_SOP_05, version 02, 15.08.2015

³ SOP Statistical data validation, CS_STA_SOP_02, version 02, 15.08.2015

⁴ Klingenberg, B. 2014. A new and improved confidence interval for the Mantel–Haenszel risk difference. *Statistics in medicine*, 33(17): 2968.

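### Deaths recorded at the day-3 and day-14 calls count as outcome events, but only the intervention arm gets those calls; any death that day 30 misses is therefore counted unequally between arms

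*SAP*

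**What the plan says.** Section 6.2, Table 8, builds the primary outcome from five terms joined by OR: not discharged alive, death as the reason the day-3 call failed ("reas_pat_notre_d3==Death or"), the same for day 14 ("reas_pat_notre_d14==Death or"), `death_d30`, and at least one unplanned readmission. The two call variables are also listed for the 30-day death outcome. The call death dates (`date_death_d3`, `date_death_d14`) enter the time-to-event outcome and the offset for count outcomes.

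Section 5.6 says that the procedural data, which include the calls, "are collected for the transition care group only". Section 7, Table 10, gives as its reason for dropping the blinded analysis that "only patients in the intervention group have follow up phone calls".

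Section 6.4 handles patients without outcome information: "Therefore, we will assume that drop-outs did not have a readmission and did not die". The same section treats death separately and states that it causes no missing data for the primary outcome, 30-day deaths or time to the primary outcome.

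On the day-30 assessment, section 2.8 says that "the study nurses collecting the outcomes or working on data cleaning will be blinded to the group allocation".

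**The concern.** After discharge, a death in the intervention arm can reach the analysis through three forms: the two calls and the day-30 form. A death in the control arm can reach it through the day-30 form only. This does no harm while the day-30 form is complete, because a death seen at a call is then also recorded as `death_d30`.

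It matters when the day-30 form is missing. The drop-out rule in section 6.4 then turns unequal search into unequal counting. Two patients with the same course, dead by day 14 and with no day-30 form, are coded differently because of their arm.

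At stake are the primary outcome and, in larger proportion, the 30-day death outcome. Section 6.5 plans no safety evaluation, so the death comparison is the main place where an excess of deaths would show. Unplanned readmissions come from the day-30 form in both arms and are not affected.

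**Working it through.** **1. The plan's own figure.** Section 2.3 gives 27% in control, a 25% relative reduction (0.27 × 0.75 = 20.25%), 80% power and 10% loss; section 4.2 sets 5%, two-sided. With pooled variance under the null and mean proportion 0.23625:

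n = [1.960 × √(2 × 0.23625 × 0.76375) + 0.842 × √(0.27 × 0.73 + 0.2025 × 0.7975)]² / 0.0675² = 620.5, so 621 per arm.

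621 / 0.9 = 690 per arm, 1,380 in total. The stated sample size is reproduced, and this point does not change it.

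**2. Where the coding differs.** A patient who dies after discharge and by day 14, with no unplanned readmission recorded:

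| Day-30 form | Intervention, death recorded at a call | Control |
|---|---|---|
| Present, records the death | event | event |
| Missing | event (Table 8) | no event (section 6.4) |

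Only the second row differs. When the form is missing, readmissions are missing too, so the death alone decides the coding.

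**3. Size.** Bias in the risk difference = m × f × g × c, where
- m = 30-day mortality, assumed 3% to 5%;
- f = share of deaths without a day-30 form, assumed 10% to 30%, or 0 if day 30 captures every death;
- g = share of deaths by day 14, assumed 14/30 = 0.467 (even spread over 30 days);
- c = share of those deaths that a call records, set to 1, the upper limit.

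The SAP gives none of these four.

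- f = 0: bias 0.
- Low: 0.03 × 0.10 × 0.467 = 0.14 points; 690 × 0.0014 = 1.0 death per arm; 0.14 / 6.75 = 2% of the planned difference.
- High: 0.05 × 0.30 × 0.467 = 0.70 points; 690 × 0.007 = 4.8 deaths per arm; 0.70 / 6.75 = 10% of the planned difference.

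The standard error of the planned risk difference is √[(0.27 × 0.73 + 0.2025 × 0.7975) / 690] = 2.28 points. The bias is thus 0 to about 0.3 standard errors (0.70 / 2.28).

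For 30-day death, the share of control deaths lost relative to the intervention arm is f × g × c: 0.10 × 0.467 = 5% to 0.30 × 0.467 = 14%, whatever the mortality.

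**4. Effect on the primary test.** Here 690 per arm are analysed, because section 6.4 keeps drop-outs in. The control rate is lowered by the bias b and the intervention rate held at 20.25%. Power = Φ{[d − 1.960 × √(2p̄q̄/690)] / √[(p₁q₁ + p₂q₂)/690]}, with p₁ = 0.27 − b, p₂ = 0.2025, d = p₁ − p₂, p̄ the mean of the two and q = 1 − p.

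| b (points) | Observed difference | Power |
|---|---|---|
| 0 | −6.75 | 84.0% |
| 0.14 | −6.61 | 82.5% |
| 0.25 | −6.50 | 81.3% |
| 0.50 | −6.25 | 78.4% |
| 0.70 | −6.05 | 75.8% |

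With no true effect (27% in both arms), the two-sided rejection rate would be 5.1% at 0.25 points and 5.5% at 0.50 points, with the excess on the side of apparent harm.

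**The case against.** The strongest reply is that the SAP treats deaths as known. Section 6.4 says that death does not lead to missing data for these outcomes, and the no-event rule is written for drop-outs. How vital status is sought at day 30 for a patient who cannot be reached is follow-up conduct that the protocol may well set. If `death_d30` is already completed from next of kin, physicians or hospital records in both arms, the extra call terms change nothing in the binary outcomes. This stands, and it is why zero belongs in the range. But it is an assumption about completeness. Table 8 does not depend on it, and the SAP does not say how a control patient not reached at day 30 is shown to be alive.

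The sizes above also lean high. They let the calls find every early death, although Table 7 allows a call to end with no answer, and they assume that a death discoverable by day 14 can be missed at day 30. That also stands.

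A third reply is that combining every form on which a death is recorded is a reasonable completeness rule. It is, and the remedy must not turn a documented death into a survival. The fault is that the rule draws on sources that one arm lacks.

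Finally, section 6.4 already plans multiple imputation of the primary outcome. That analysis runs only if drop-outs exceed 5%, and it is not described as removing call-based deaths. None of the analyses in section 6.3.3 restricts death to common sources.

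**Conclusion.** The asymmetry in the derivation is plain from the text; its effect is conditional. It is zero if day 30 captures all deaths. Otherwise it is probably small: 0 to 0.7 points on the primary outcome under the assumed inputs, with a larger relative effect on 30-day death. On these two outcomes the direction is against the intervention, so it can dilute a benefit or suggest excess deaths. For the time-to-event and count analyses the effect passes through event dates and person-time, and it is not sized here.

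Three stronger readings are tempting, and the SAP does not support them.
- A reader might infer that the comparison is certainly biased. That needs deaths missed at day 30, and the SAP gives no number of them.
- A reader might infer a serious loss of power. A bias of 2.5 points would bring power to 47.4%, but it requires 10% of controls without day-30 data and a quarter of those dead by day 14. Section 6.4 expects few drop-outs, and nothing in the SAP supports the second figure.
- A reader might take this as independent of the drop-out rule. It is not: coding drop-outs as event-free is what makes unequal search count. The two should be resolved together.

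**What to change.** Before database lock:

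1. Complete `death_d30` and `date_death_d30` for every randomised patient in both arms, including those not reached at day 30 and those whose death was recorded at a call. Use the same sources in both arms; those that Table 7 lists for call-recorded deaths (next of kin, treating physician, hospital, death certificate) would serve. The blinded outcome nurses should do this from a list that shows neither arm nor call entries.
2. In Table 8, derive death after discharge from these two variables for the primary outcome, 30-day death, time to event and the count offset. Keep any documented death as a death, whatever its source.
3. Report by arm the number of deaths known only from the calls.
4. Add a sensitivity analysis of the primary outcome and 30-day death that counts only deaths ascertainable from sources available in both arms.
5. Revise this together with the drop-out rule in section 6.4, so that a control patient with unknown vital status is not set to alive by default while the other arm has extra information.

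The cost is some record checks for patients not reached, revised wording in Table 8 and section 6.4, and one extra analysis. The rule should be fixed before lock because the statistician is not blinded.
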